## 2.2.3 Exploratory Endpoints

VC02-101 and VC02-102 Exploratory Endpoints/ Cohort 1 and 2:

• Histological results of explanted units and any associated tissue capsule as evaluated for cell viability, vascularization, immune response, and/or cell maturation and differentiation.

## 3. INVESTIGATIONAL PLAN

#### 3.1 Study Design

This Phase 1/2, first-in-human clinical trial is comprised of two study protocols: VC02-101 and VC02-102.

The VC02-101 study will be an open-label, FIH, clinical trial in subjects with T1DM and HU. Two cohorts are planned for enrollment in this trial, with enrollment of Cohort 1 occurring prior to enrollment of Cohort 2.

All VC02-101 enrolled subjects will have up to one or more VC-02-300 units and/or one or more smaller VC-02-20 (sentinel) units implanted in anatomical locations involving the trunk or extremities (e.g., back, flanks, arms, legs, and abdomen) suitable for implantation, as deemed appropriate by the Investigator and/or Surgeon after consultation with the Sponsor. Documentation of the implant plan for a subject will be provided to the Investigator by the Sponsor. Implantation will be executed under an anesthetic with or without sedation. The following are the maximum units that can be implanted per cohort:

- In Cohort 1, subjects are implanted with up to two (2) VC-02-300 units and up to six (6) sentinels; or up to ten (10) sentinels only.
- In Cohort 2, subjects are implanted with up to twelve (12) units. Of the twelve implanted units, no more than ten (10) will be VC-02-300 units, and the remainder will be VC-02-20 units. For example, if ten (10) VC-02-300 units are implanted, up to two (2) sentinels may also be implanted.

The VC02-102 study will be an open-label clinical trial in otherwise healthy subjects with T1DM. All subjects enrolled in Protocol VC02-102 are considered part of Cohort 1 for analysis purposes.

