## 2.1. Study Objectives

There are two distinct cohorts in this FIH trial, and the cohorts serve different objectives.

Cohort 1 Study Objectives:

- Assess the local and systemic safety and tolerability of VC-02 combination product when implanted into subjects with T1DM and HU.
- Assess histological proof of mechanism for VC-02 combination product (e.g., cell survival and differentiation to beta cells).

Cohort 2 Study Objectives:

- Evaluate the clinical efficacy and further assess safety and tolerability of VC-02 combination product from implantation to Month 24.
- Explore effects of weight, gender, BMI, or other potentially interacting factors on the responsiveness of the subjects to the experimental intervention.

Exploratory Objectives (Cohorts 1 & 2):

- Optimize the recommended surgical implantation procedure, anatomical location, and perioperative care for VC-02.
- Assess the effects of the host immune response to implanted VC-02 units.

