8.0 (Amendment #9) 18 May 2020	3.1	Changed the number of implants per subject in VC02-101 to "twelve (12) units. Of the twelve implanted units, no more than four ten (104) will be VC-02-300 units, and the remainder will be VC-02-20 units. For example, if ten (10) VC-02-300 units are implanted, up to two (2) sentinels may also be implanted."	The number of implants was changed in VC02-101 Protocol Version 8.0 (Amendment #9).
		Removed language about implants in VC02-102 subjects.	Only three subjects were enrolled in the VC02-102 study.
8.0 (Amendment #9) 18 May 2020	3.2.1	Changed the number of subjects enrolled in Cohort 2 from "40" to "60", and the total number of subjects enrolled to "75".	The number of implants was changed in VC02-101 Protocol Version 8.0 (Amendment #9).
8.0 (Amendment #9)	3.2.3	Updated description of the number of implants in VC02-101 Cohort 1 and Cohort 2 subjects,	The number of implants was changed in VC02-101 Protocol Version 8.0 (Amendment #9).

Protocol Version # Date	SAP Section	Modification	Description and Rationale
18 May 2020		the duration of the study, and the number of subjects enrolled in Cohort 2 as well as overall.	
8.0 (Amendment #9) 18 May 2020	4.2	Updated the definition of the FAS to exclude subjects enrolled in VC02-101 Cohort 1 or VC02- 102 Cohort 1.	The FAS was updated in VC02-101 Protocol Version 8.0 (Amendment #9).
8.0 (Amendment #9) 18 May 2020	4.3	Updated the SAP Windows for the visits Week 104 and Week 105 (Follow-Up Visit).	The Week 104 visit did not need an upper range since it is the last visit of the study. The Week 105 (Follow-Up Visit) did not need SAP Windows.
8.0 (Amendment #9) 18 May 2020	4.4	Added analysis rules for dropouts and missing data for MMTTs and rules for determining TEAEs using missing or partial dates.	Clarified based on safety deliverables.
8.0 (Amendment #9) 18 May 2020	4.6.1	Updated derivations and visits for the analysis of the 2-hour MMTTs	The 2-hour MMTT visits were changed in VC02-101 Protocol Version 8.0 (Amendment #9).
8.0 (Amendment #9) 18 May 2020	4.6.2	Removed language pertaining to subjects who do not complete the 2-hour MMTT.	The C-peptide must be measurable to perform the analysis.
8.0 (Amendment #9) 18 May 2020	4.6.3	Updated the derivation for baseline average weekly frequencies of subject-reported HEs. Added statement "Data should	Clarified based interim safety summaries. The number of implants was changed in VC02-101 Protocol

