## 1. INTRODUCTION

This Phase 1/2, first-in-human clinical trial is comprised of two study protocols: VC02-101 and VC02-102. It will assess whether VC-02 can be implanted and maintained safely for up to two years in type 1 diabetes mellitus (T1DM) subjects with hypoglycemia unawareness (HU) in VC02-101, and for up to four months in otherwise healthy T1DM subjects in VC02-102. During the first three to six months, VC-02 is expected to vascularize adequately, and pancreatic progenitor cells are expected to differentiate into mature glucose-responsive, insulin-producing cells, capable of secreting insulin in response to serum glucose levels.

Diabetes mellitus, defined by the loss of metabolic glycemic control, is a tremendous healthcare issue. While exogenous pharmaceutical insulin and adjunct medicines can alleviate hyperglycemia, and when managed properly, prevent serious life-threatening excursions in blood glucose levels, it is far from a perfect solution. The natural history of T1DM presents acute and chronic health risks to all affected patients. Controlling the disease with insulin self-administration carries the acute risk of hypoglycemic events (HE) and even death, and the need for constant vigilance and testing results in a significant degradation of quality of life for the patient (and often, their families). Moreover, controlling the short-term challenges of diabetes with monitoring and insulin does not prevent the serious long-term sequelae of diabetes. These long-term sequelae include microvascular complications, such as peripheral and autonomic neuropathies, nephropathies, retinopathy, and diminished wound healing, as well as macrovascular complications and cardiovascular disease.

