Cohort 1 subject. Sentinels and/or VC-02-300 units may be explanted at various time points postimplant to assess the status of cell viability and differentiation, vascularization, and the host response. Including the requirements of the screening period, Cohort 1 subjects will complete a total of 18 study visits spanning approximately 25 months. The total duration of treatment (implantation) may be up to four (4) months for each VC02-102 Cohort 1 subject. Sentinels may be explanted at various time points post-implant to assess the status of cell viability and differentiation, vascularization, and the host response. Any remaining units will be explanted at Week 16 (four months).

At the end of the treatment period for each subject enrolled under the VC02-101 and VC02-102 protocols, all remaining implanted units will be removed, and the subject will be required to participate in a separate, one-year, follow-up, non-interventional, observational study. The primary purpose of this additional study is to ensure there are no long-term safety issues associated with previous implantation with VC-02.

[figure not shown]

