#### 4. GENERAL CONSIDERATIONS FOR DATA ANALYSIS

The phrase "treatment group" is used in this section to denote the number of initially implanted VC-02-300 units. If a subject has a VC-02-300 unit explanted for any reason and remains in the study, then he/she will be included in the treatment group that is described by the number of VC-02-300 units originally implanted. If no VC-02-300 units are implanted, but sentinel units are implanted, then the subject will be included in the "0 implanted VC-02-300 units" treatment group. If, during the study, the number of sentinels implanted in subjects who do not have VC-02-300 units varies widely (e.g., one subject has one sentinel unit implanted while another subject has 10 sentinel units implanted), the "zero VC-02-300 unit" treatment group may be further broken out by the number of sentinels implanted.

As the VC02-101 and VC02-102 studies collectively represent the first-in-human trial, there are no statistical hypotheses regarding treatment effects. Rather, displays and comparisons of study results – regarding safety and efficacy among the treatment groups – will primarily utilize descriptive statistics, as noted below.

Unless otherwise specified, continuous variables will be summarized by presenting the number of

non-missing observations, mean, standard deviation, median, minimum, and maximum. Categorical variables will be summarized by presenting the number of subjects and percentage for each category.

Summary results will be provided for each cohort and treatment group as well as overall.

All tabulations will be based on pooled data across centers.

Analyses will be performed using SAS for Windows statistical software, version 9.4 or higher (SAS, Cary, NC), except where other software may be deemed more appropriate.

CTI Clinical Trial and Consulting Services will perform all efficacy and safety statistical analyses.

Subject data will be listed, sorted by protocol, cohort, treatment group (number of VC02-300 units and ascending VC02-20/sentinel units [if applicable]), and subject number.

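### Cohort 1 adverse event percentages pool the three VC02-102 subjects with VC02-101 Cohort 1, although the other three parts of the same primary endpoint do not

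*SAP*

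**What the plan says.** **Populations.** SAP 3.1 describes the two protocols differently: "The VC02-101 study will be an open-label, FIH, clinical trial in subjects with T1DM and HU" and "The VC02-102 study will be an open-label clinical trial in otherwise healthy subjects with T1DM". The Cohort 1 objective in Protocol 2.1 is to "Assess the local and systemic safety and tolerability of VC-02 combination product when implanted into subjects with T1DM and HU". SAP 2.1.1 gives VC02-102 its own parallel objective, for T1DM without mention of hypoglycemia unawareness (HU).

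**Pooling rule.** SAP 3.1: "All subjects enrolled in Protocol VC02-102 are considered part of Cohort 1 for analysis purposes". SAP 4.2 repeats the rule and draws the safety set from both protocols. The safety set in Protocol 10.4.1 covers subjects enrolled in that study and does not mention VC02-102.

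**Exposure.** SAP 3.2.3: "The total duration of treatment (implantation) may be up to four (4) months for each VC02-102 Cohort 1 subject", with any remaining units removed at Week 16. Protocol 3.1 and SAP 3.2.3 allow VC02-101 Cohort 1 up to two years. SAP 3.2.3 also says that VC02-102 subjects receive no VC-02-300 units, so all of them fall in the 0-unit treatment group.

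**Number.** The SAP revision table records: "Only three subjects were enrolled in the VC02-102 study".

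**Tabulation.** SAP 4: "Summary results will be provided for each cohort and treatment group as well as overall". SAP 7.2.7 defines TEAE incidence as subjects with the event divided by subjects in the safety set. It plans no split by protocol and no exposure-adjusted rate. In contrast, SAP 7.6.1 (off-target growth), 7.6.2 (immune sensitization) and 7.6.3 (implant tolerability) each count only subjects enrolled in VC02-101 Cohort 1.

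**The concern.** The incidence of adverse events related to product, surgery or immunosuppression is the first of four components of the Cohort 1 primary endpoint (Protocol 2.2.1, SAP 2.2.1). As planned, this component has a pooled denominator and the other three have a VC02-101 denominator. SAP 7.6.3 counts product- and surgery-related adverse events as tolerability findings, so one event type can appear over two different denominators within one primary endpoint.

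The pooled Cohort 1 percentage also answers neither of the two objectives in SAP 2.1.1 separately. A crude proportion takes no account of time at risk, so subjects implanted for at most 16 weeks count the same as subjects implanted for up to 104. For events that accrue late, such as those of long-term immunosuppression, this can make a first-in-human safety figure look better than the long-exposure group alone would show. It also affects any reading of the 0-unit group against the 1- and 2-unit groups.

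**Working it through.** The plan states no adverse event rate and no precision target for Cohort 1, so there is no figure of its own to reproduce.

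**Inputs from the documents**
- VC02-102 subjects: 3 (SAP revision table).
- VC02-101 Cohort 1 size n: 3 to 15 (Protocol 4.1). SAP 3.2.1 does not say whether the cap of 15 includes VC02-102; if it does, the largest n is 12.
- Maximum implantation: 16 weeks for VC02-102 and 104 weeks for VC02-101 (SAP 3.2.3).

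**Assumptions, not in the documents**
- 104-week incidence p104 between 10% and 80%.
- Constant hazard, equal in both protocols.
- Every subject implanted for the maximum time.
- The denominator in each column is the safety-set subjects in that column.

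**Step 1: weight of VC02-102 in pooled Cohort 1.** The share of subjects is 3/(n+3). The share of implant time is 3×16/(3×16 + 104n) = 48/(48 + 104n). Mean maximum exposure is (104n + 48)/(n+3).

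| n | Share of subjects | Share of implant time | Mean maximum weeks | One subject is worth |
|---|---|---|---|---|
| 3 | 3/6 = 50% | 48/360 = 13.3% | 60.0 | 16.7 points |
| 12 | 3/15 = 20% | 48/1296 = 3.7% | 86.4 | 6.7 points |
| 15 | 3/18 = 16.7% | 48/1608 = 3.0% | 89.3 | 5.6 points |

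Under Protocol 3.1 the first three VC02-101 Cohort 1 subjects also receive no VC-02-300 units. VC02-102 can therefore be up to 3/6 of the 0-unit group, however large Cohort 1 becomes.

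**Step 2: incidence at 16 weeks.** p16 = 1 − (1 − p104)^(16/104). For p104 = 10%, 30%, 50% and 80%, p16 = 1.6%, 5.3%, 10.1% and 21.9%.

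**Step 3: pooled incidence.** Pooled = (n×p104 + 3×p16)/(n+3). Example with n = 15 and p104 = 50%: (15×0.50 + 3×0.101)/18 = 0.434, which is 6.6 points low.

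| p104 | n = 3 | n = 12 | n = 15 |
|---|---|---|---|
| 10% | 5.8% (−4.2) | 8.3% (−1.7) | 8.6% (−1.4) |
| 30% | 17.7% (−12.3) | 25.1% (−4.9) | 25.9% (−4.1) |
| 50% | 30.1% (−19.9) | 42.0% (−8.0) | 43.4% (−6.6) |
| 80% | 51.0% (−29.0) | 68.4% (−11.6) | 70.3% (−9.7) |

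**Step 4: early events.** If an event can occur only in the first 16 weeks, p16 = p104 under equal hazards, and the pooled figure equals p104. The exposure difference then has no effect.

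**Step 5: check on the 104 weeks.** The window table in SAP 4.3 gives Cohort 1 a Week 17 follow-up visit and heads the later visits as Cohort 2 only. Read alone, this would put both protocols on the same short schedule. SAP 3.2.3, Protocol 3.1 and the common visit schedule in Protocol 6 say otherwise for VC02-101 Cohort 1. These passages must be reconciled; the working follows the latter three.

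**The case against.** The strongest case for leaving the plan alone is this. The pooling is explicit. The SAP treats the two protocols together as the first-in-human trial and writes the Cohort 1 endpoint jointly for both (SAP 2.2.1). Protocol 10 allows the SAP to modify the protocol's analysis, and a single-study protocol would not be expected to name a sister study in its safety set. No hypothesis is tested, and only three subjects are involved. Exposure duration is summarised by cohort and treatment group (SAP 7.1), and every adverse event is listed with its study day of onset.

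Most of this stands, and it limits the point to a matter of presentation. It does not explain why one component of a jointly written endpoint is pooled and three are not. Nor does the listing fully repair the table: the general rule in SAP 4 sorts listings by protocol, but the sort order given for the adverse event listing in SAP 7.2.7 does not include protocol.

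A reader might infer three stronger things, which the documents do not support:
- *That the Cohort 1 primary endpoint as a whole is contaminated.* SAP 7.6.1 to 7.6.3 already exclude VC02-102 from three of its four components.
- *That Cohort 1 no longer describes the HU population.* VC02-101 is not strictly an HU population, because inclusion criterion 10 also admits significant glycemic lability. The eligibility criteria of VC02-102 are not in these documents, so whether its subjects lacked HU is itself an inference. The 1- and 2-unit groups contain VC02-101 subjects only.
- *That pooling must lower the percentages.* That needs late-accruing events and long VC02-101 exposure. Two years is a maximum, and the Sponsor sets the explant times. Surgery, induction, etanercept and the short steroid course all fall early, so events tied to them may show no dilution from exposure.

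**Conclusion.** The point holds in a limited form. The TEAE percentages for the Cohort 1 total and the Cohort 1 0-unit group combine two populations with maximum exposures of 16 and 104 weeks, and the related-event component of the primary endpoint uses a different denominator from the other three. This follows from the text alone and needs no assumption.

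The size of any dilution does depend on assumptions. With a constant hazard and full exposure it is about 1.4 to 9.7 points at 15 VC02-101 subjects, 1.7 to 11.6 at 12, and 4.2 to 29 at 3, for 104-week incidences of 10% to 80%. At the upper sizes this is of the order of one or two subjects. It is material mainly if Cohort 1 stays near its minimum, or within the 0-unit group. For events confined to the first 16 weeks it is nil as far as exposure is concerned. The change is worth making because it is cheap and clarifies a primary safety figure, not because the planned tables would be invalid.

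**What to change.** In SAP 7.2.7, with matching wording in 3.1, 4 and 4.2:
- Show VC02-101 Cohort 1 and VC02-102 as separate columns in the TEAE and treatment-emergent SAE tables, including within the 0-unit group.
- Use VC02-101 Cohort 1 alone as the denominator for its related-event primary component, as SAP 7.6 already does for the other three.
- Pool the two protocols only in the overall column.

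Events per subject-year, from the durations already derived in SAP 7.1, would be a useful optional supplement for the larger groups. A separate rate for VC02-102 would be too unstable to interpret, since 3×16 = 48 subject-weeks is 48/52 = 0.92 subject-years.

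The cost is SAP wording and one extra column, with no new data, since protocol is already a listing sort variable. The downside is a smaller 0-unit denominator, with three subjects fewer than in the pooled table.

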#### 3.2 Treatment

#### 32.1 Randomization Scheme and Treatment Arm Assignment

There is no randomization scheme for this study. Subjects will be summarized by cohort and treatment group (the number of initially implanted VC-02-300 units). If, during the study, the number of sentinels implanted in subjects who do not have VC-02-300 units varies widely (e.g., one subject has one sentinel unit implanted while another subject has 10 sentinel units implanted), the "zero VC-02-300 unit" treatment group may be further broken out by the number of sentinels implanted.

A minimum of three (3) and up to 15 subjects total will be enrolled in Cohort 1 at one (1) or more sites. Cohort 2 will enroll up to 60 subjects from up to ten (10) sites. Therefore, the total enrollment possible for the trial (Cohort 1 and Cohort 2) is up to 75 subjects.

#### 3.2.2 Blinding

There is no blinding since this study is open-label.

#### **323 Dosing Schedule**

#### VC02-101 and VC02-102 Cohort 1:

At a minimum, the first three (3) subjects in Cohort 1 will be enrolled sequentially in order to assess safety and tolerability data thru Week 2 before implanting the next subject. For example, data thru Week 2 from the first subject will be formally reviewed by the Sponsor prior to allowing the Investigator to implant the next subject. If a treatment-related serious adverse event (SAE) is observed within the first two weeks in the subject, the implantation of the next subject will be postponed until consultation between the Sponsor and Investigator has devised appropriate safeguards. Overall, if no treatment-related SAEs are observed with the first three (3) subjects after each has reached Week 4, additional Cohort 1 enrollment may then be performed in parallel.

[figure not shown]
Initially, up to six sentinels will be implanted in the first three (3) Cohort 1 subjects in order to provide sufficient histologic data to assess preliminary safety and tolerability. The first three (3) subjects enrolled in Cohort 1 will not be implanted with VC-02-300 units. After the first three subjects are enrolled in Cohort 1 and initial safety and tolerability is confirmed, VC-02-300 units may then be implanted in subsequent, enrolled subjects and the stimulated C-peptide levels will be monitored. These additional Cohort 1 subjects may be implanted with up to two (2) VC-02-300 units and up to six (6) VC-02 sentinels total. The decision as to the number of VC-02-300 units implanted in subsequent subjects will be data-driven and this number may be reduced. However, if no VC-02-300 units are implanted in these additional; Cohort 1 subjects, up to ten (10) VC-02 sentinels may instead be implanted. No subjects enrolled in VC02-102 will receive VC-02 300 units and will have up to six smaller, VC-02-20 (sentinel) units implanted in anatomical locations involving the trunk or extremities (e.g., back, flanks, arms, legs, and abdomen) suitable for implantation, as deemed appropriate by the Investigator and/or Surgeon after consultation with the Sponsor. Documentation of the implant plan for a subject will be provided to the Investigator by the Sponsor. Implantation will be executed under an anesthetic with or without sedation.

The total duration of treatment (implantation) may be up to two (2) years for each VC02-101

Cohort 1 subject. Sentinels and/or VC-02-300 units may be explanted at various time points postimplant to assess the status of cell viability and differentiation, vascularization, and the host response. Including the requirements of the screening period, Cohort 1 subjects will complete a total of 18 study visits spanning approximately 25 months. The total duration of treatment (implantation) may be up to four (4) months for each VC02-102 Cohort 1 subject. Sentinels may be explanted at various time points post-implant to assess the status of cell viability and differentiation, vascularization, and the host response. Any remaining units will be explanted at Week 16 (four months).

At the end of the treatment period for each subject enrolled under the VC02-101 and VC02-102 protocols, all remaining implanted units will be removed, and the subject will be required to participate in a separate, one-year, follow-up, non-interventional, observational study. The primary purpose of this additional study is to ensure there are no long-term safety issues associated with previous implantation with VC-02.

[figure not shown]

